6. RESEARCH QUESTION AND OBJECTIVES

6.1. Safety Specifications

Important Identified Risks:

- · Hyperkalaemia
- Events related to hypotension

Important Potential Risks:

- · Renal impairment
- Concomitant use of CYP3A4 inhibitor

Important Missing Information:

- · Safety in the diabetes patients with micro albuminuria or proteinuria
- · Safety in the patients with renal impairment

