7.3.4.1.1. Relevant drugs

- · Diuretics (excluding potassium-conserving diuretics)
- · Potassium-conserving diuretic (*contraindication for concomitant use) a)
- · Angiotensin-converting enzyme (ACE) inhibitors b)
- · Angiotensin II receptor blockers (ARB) b)
- β blockers
- Ca antagonists
- Other antihypertensive drugs (α blockers, direct renin inhibitors, etc.)
- Digitalis preparations
- Antiarrhythmic drugs
- Antiplatelet drugs
- Oral anticoagulant drugs
- Statin drugs
- Itraconazole (*contraindication for concomitant use) c)
- Ritonavir (*contraindication for concomitant use) c)
- Nelfinavir (*contraindication for concomitant use) c)
- Other CYP3A4 inhibitors b)
- · Aliskiren b), d)
- Cyclosporin b)
- Tacrolimus b)
- · Drospirenone b)
- · Nonsteroidal anti-inflammatory drugs (NSAIDs) e)
- Potassium preparations b)
- a. Contraindicated concomitant drugs (When they are used concomitantly, the potassium-retaining action may be potentiated, thereby possibly elevating the serum potassium level)
- b. Concomitant drugs requiring caution (When they are used concomitantly, the potassium-retaining action may be potentiated, thereby possibly elevating the serum potassium level)

- c. Contraindicated concomitant drugs (Potent CYP3A4 inhibitors inhibit the metabolism of this drug, and consequently the plasma concentration of this drug may be elevated, thereby possibly inducing an elevation in the serum potassium level)
- d. Describe in the section of other antihypertensive drugs (α blockers, direct renin inhibitors, etc.).
- e. Concomitant drugs requiring caution (Clear mechanisms are unknown, but when the production of prostaglandin is suppressed, the sodium-retaining action may diminish the antihypertensive action, and the potassium-retaining action may elevate the serum potassium level. The occurrence of severe hyperkalaemia was reported in patients with renal impairment when they were used concomitantly.)

7.3.4.2. Other previous treatment drugs and concomitant drugs (Collect information for subjects who have any adverse event corresponding to "renal impairment")

If any adverse event corresponding to "renal impairment" is observed, select the presence/absence of treatment with drugs other than this drug and "7.3.4.1.1. Relevant drugs" from among drugs used between three months before the start date of administration and the last day of the observation period.

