5.4. Subgroup Analyses

The safety of study drug will be analyzed for each of the subgroups defined according to the following patient characteristics. The underlined one in each categorization will be used as the reference when a risk ratio is calculated:

- Hepatic impairment (as assessed by the physician) (present, absent, unknown)
- Renal impairment (as assessed by the physician) (present, absent, unknown)
- Estimated creatinine clearance (eCLCr)
 (<30 mL/min, 30 mL/min <50 mL/min, ≥50 mL/min, unknown)
- Not aged (<65 years old), Aged (≥65 years old)
- Children (<15 years old), Not children (≥15 years old)
- Young-old (\geq 65, <75 years old), Old-old + oldest-old (\geq 75 years old)
- Diabetes mellitus with microalbuminuria or proteinuria (present, absent, unknown)

Safety will also be analyzed for each of the subgroups defined according to the following factors:

- Use of a relevant treatment for CHF/hypertension (present, absent) (any of the 1st to 17th drug groups, except the 2nd and 15th which are contraindicated for coadministration, listed)
- Previous treatment with device therapy (present, absent, unknown)

NYHA class (I, II, III, IV, not assessed/unknown)

As a subgroup analysis, patients who may have violated any of the contraindications indicated in the package insert of Selara Tablets ("contraindication violators", hereinafter) will be extracted according to the criteria defined separately and the safety will be assessed for this subgroup.

The effectiveness of study drug will be analyzed for each of the subgroups defined according to the following patient characteristics:

- Hepatic impairment (as assessed by the physician) (present, absent, unknown)
- Renal impairment (as assessed by the physician) (present, absent, unknown)
- Estimated creatinine clearance (eCLCr)
 (<30 mL/min, 30 mL/min <50 mL/min, ≥50 mL/min, unknown)
- Not aged (<65 years old), Aged (≥65 years old)
- Children (<15 years old), Not children (≥15 years old)
- Young-old (\geq 65, <75 years old), Old-old + oldest-old (\geq 75 years old)
- Use of a relevant treatment for CHF/hypertension (present, absent)
- NYHA class (I, II, III, IV, not assessed/unknown)
- Treatment status (completed, discontinued)

If patients included in a subgroup for safety or effectiveness analysis are limited, reviewing individual patients will be considered instead of presenting a statistical summarization.

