To investigate the relationship between treatments for CHF/hypertension, or CYP3A4 inhibitors/other concomitant drugs requiring caution (any drug in the 3rd, 4th, 13th, 14th, 16th, or 17th drug groups, or a liskiren included in the 7th, listed) and adverse reactions of hyperkalaemia, hypotension-related events, or renal impairment-related events, patients experiencing hyperkalaemia, hypotension-related events, and renal impairment-related events will be summarized by PT in terms of number of patients, depending on whether they used CHF/hypertension treatments or whether they used CYP3A4 inhibitors/other concomitant drugs requiring caution (any drug in the 3rd, 4th, 13th, 14th, 16th, or 17th drug groups, or aliskiren included in the 7th, listed). Concomitant drugs used after the first onset of the relevant event will be excluded from the summarization.

• Adverse Reactions in Patients Excluded from the Safety Analysis Set

Adverse reactions occurring in CRF-collected patients who are excluded from the Safety Analysis Set will be presented in a tabular form. In addition, they will be summarized by SOC and PT in terms of number of patients.

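### The SAP's concomitant-drug table omits contraindicated drug groups 2 and 15 from its exposure set, so it cannot show reactions with those drugs and can count their users as unexposed

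*SAP*

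**What the plan says.** SAP 8.2.3.1, in its item on concomitant drugs and adverse reactions, looks at hyperkalaemia, hypotension-related and renal impairment-related reactions against two drug factors. One is treatment for CHF/hypertension. The other is "whether they used CYP3A4 inhibitors/other concomitant drugs requiring caution (any drug in the 3rd, 4th, 13th, 14th, 16th, or 17th drug groups", with aliskiren from the 7th group added. Results are given by preferred term "in terms of number of patients, depending on whether they used CHF/hypertension treatments" or drugs in the second set. The only exclusion stated there is one of timing: drugs used after first onset do not count.

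SAP 5.4 defines the CHF/hypertension factor as "any of the 1st to 17th drug groups, except the 2nd and 15th which are contraindicated for coadministration, listed". Its absent level is underlined as the reference, and 8.2.3.4 calculates risk ratios for binary categorisations of this kind.

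Protocol 7.3.4.1.1 lists the drugs collected and marks four entries as contraindicated: potassium-conserving diuretics, itraconazole, ritonavir and nelfinavir. Its footnote a says the first may raise serum potassium through potassium retention. Its footnote c covers the other three: "Potent CYP3A4 inhibitors inhibit the metabolism of this drug, and consequently the plasma concentration of this drug may be elevated", again with a possible rise in potassium. Protocol 6.1 lists "Concomitant use of CYP3A4 inhibitor" as an important potential risk and hyperkalaemia as an important identified risk.

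**The concern.** The second factor in 8.2.3.1 carries CYP3A4 inhibitors in its name, but the groups that define it leave out both groups that the SAP calls contraindicated. Nothing in the section takes users of those groups off the non-use side. A hyperkalaemia case on a potassium-conserving diuretic or a potent CYP3A4 inhibitor can therefore be printed as a case without an interacting drug. At stake is whether the one table meant to relate concomitant drugs to these reactions can say anything about drugs that the protocol itself singles out for raising potassium, one class of which belongs to a named risk.

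**Working it through.** The plan gives no figure for this point, so the check is set membership followed by a rough scale.

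**Inputs**
- Exposure set in SAP 8.2.3.1: E = {3, 4, 13, 14, 16, 17, aliskiren within 7}.
- Contraindicated groups in SAP 5.4: C = {2, 15}.
- CHF/hypertension set in SAP 5.4: H = {1, ..., 17} without {2, 15}, that is 17 − 2 = 15 groups.

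**Step 1: what groups 2 and 15 are.** The SAP's 17-group list is not in the documents. In Protocol 7.3.4.1.1 the second entry is the potassium-conserving diuretics, marked contraindicated, which fits group 2. The only other contraindicated entries are the three footnote c drugs, so group 15 is inferred to be these drugs combined. The protocol's literal order cannot be the SAP numbering. It has 22 entries against 17 groups and four contraindicated entries (2, 13, 14, 15) against two. It also puts aliskiren 17th, where the SAP puts it in the 7th, in agreement with protocol footnote d.

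**Step 2: overlap.** E and C share no group, and H and C share no group.

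**Step 3: where a user of group 2 or 15 lands.**

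| Other listed drugs taken | 8.2.3.1 caution/CYP3A4 factor | 5.4 CHF/hypertension factor |
|---|---|---|
| None | non-use | absent (reference) |
| Only groups in H outside E, such as a β blocker | non-use | present |
| An ACE inhibitor or ARB (3 or 4) | use, on account of that drug | present |

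In the first two rows the patient is misplaced in 8.2.3.1. In the third the patient is in the use column, but the contraindicated drug cannot be seen there. In no row does the table relate groups 2 and 15 to the reaction.

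**Step 4: scale.** The documents give no number of users. For orientation, the number of misplaced patients needed to yield k hyperkalaemia reactions at rate p is k / p. Protocol 7.5.2 gives p = 4.0% for all CHF patients and 8.4% for moderate renal impairment; 20% is my assumption for a higher-risk group.
- k = 1: 1/0.040 = 25; 1/0.084 ≈ 12; 1/0.20 = 5.
- k = 2: 2/0.040 = 50; 2/0.084 ≈ 24; 2/0.20 = 10.

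Against the 40 hyperkalaemia reactions expected in 1000 patients, each misplaced case is 1/40 = 2.5% of the total.

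**The case against.** The split follows the protocol's own classes: Protocol 7.3.4.1.1 separates contraindicated drugs (footnotes a and c) from drugs requiring caution (b and e), and the 8.2.3.1 factor refers to caution. Contraindicated use has its own outputs. There is a violator subgroup in 5.4, a tabulation of violators' reactions in 8.2.3.4, and violator listings in section 9. Section 9 also lists CYP3A4 inhibitor users who had reactions, without restriction to the caution class. For drugs with few users, patient listings are a reasonable choice.

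Most of this stands, and it makes the point smaller. It does not remove it. The violator outputs pool all contraindications under criteria defined elsewhere and are summarised only as necessary. The CYP3A4 listing has no comparison and does not cover potassium-conserving diuretics. Neither changes who sits on the non-use side. A deliberate split would justify separate rows, but not counting these users as unexposed.

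Two further objections also stand. ACE inhibitors and ARBs are among the standard treatments named in the indication (Protocol 7.2.1), so many users of group 2 or 15 will already be in the use column. And the absent level in 5.4 requires taking none of 15 groups; 8.2.3.4 allows its risk ratio to be dropped if a category has fewer than 10 patients and the analysis is judged difficult.

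**Conclusion.** The point holds as a minor gap in classification. As written, the 8.2.3.1 table cannot show reactions with potassium-conserving diuretics or contraindicated CYP3A4 inhibitors, and it places some of their users on the non-use side. A patient whose only listed drug is in group 2 or 15 also enters the absent reference in 5.4 and so the risk ratio in 8.2.3.4. The number of patients cannot be estimated from the documents and is probably small. The conclusion rests on reading group 15 as the footnote c drugs, which is an inference.

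A reader might infer more, and the documents do not support it:
- *That every user of these drugs is counted as unexposed.* Only those taking none of the drugs in E are.
- *That the table gives an estimate biased towards no relationship.* It gives counts of event patients, without denominators, ratio or test. Only the 5.4 factor leads to a formal ratio.
- *That NSAIDs and potassium preparations are also left out.* This needs the 22-entry order, which step 1 rules out.
- *That the hypertension survey in Protocol 6.2 shows how common such use will be.* The contraindication there was renal impairment, not a co-prescribed drug.

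**What to change.** In SAP 8.2.3.1:
- Replace the ordinal group numbers with drug names that match Protocol 7.3.4.1.1.
- Add one row for potassium-conserving diuretics and one for the contraindicated CYP3A4 inhibitors (itraconazole, ritonavir, nelfinavir).
- Define non-use as none of these drugs and no caution drug before first onset.

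In SAP 5.4, keep users of groups 2 and 15 out of the absent reference level and show them separately.

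The cost is SAP wording and recoding. Protocol 7.3.4.1 collects these drugs for all subjects, so no new data are needed. The new rows will be sparse and can be shown as counts. Because SAP version 7.0 records observation as completed, the revision history should state that the change came after data collection. It affects analysis categories only, not the clinical use of any drug.

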8.2.3.2. Adverse Events

• All Adverse Events

AEs will be summarized by SOC and PT in terms of number and proportion of patients.

• Serious/Non-Serious Adverse Events

SAEs will be summarized by SOC and PT in terms of number and proportion of patients. Non-SAEs will also be summarized in the same manner.

8.2.3.3. Other Endpoints

Observed values and changes from baseline at each Visit specified in Appendix A1.1 will be analyzed according to "8.1.1 Continuous Variables" for the following variables:

• Blood pressure (systolic, diastolic).

8.2.3.4. Subgroup Analyses

For each of the categories defined in Section 5.4, the number and proportion of patients experiencing at least one adverse reaction will be presented. For each patient category, adverse reactions will also be summarized by SOC and PT in terms of number and proportion of patients.

According to Section 8.1.3, the risk ratio of one subgroup to the other will be presented for the incidence of adverse reactions (the proportion of patients experiencing adverse reactions) for each of the binary categorizations. The risk ratio will not be presented for a categorization if <10 patients are included in one category in the categorization and the analysis of risk ratio is determined to be difficult after the categorization is reviewed.

Similar subgroup analyses will be performed also for serious adverse reactions and SAEs.

Adverse reactions occurring in contraindication violators will be tabulated and, as necessary, will be summarized by SOC and PT in terms of number and proportion of patients.

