6. ENDPOINTS AND COVARIATES

6.1. Safety Endpoints

- Adverse reactions: An adverse reaction is an AE related to study drug as judged by the physician.
- Serious adverse reactions: A serious adverse reaction is an adverse reaction that is serious as judged by the physician.
- AEs
- Serious adverse events (SAEs): A SAE is an AE that is serious as judged by the physician.
- Major investigation items: Events included in each major investigation item are defined as follows:
 - Hyperkalaemia: This includes all AEs indicated as "Hyperkalaemia-related event" or "Combination of the above two events ("Hypotension-related event" and "Hyperkalaemia-related event")" in the CRF.

Hypotension-related events: These include all AEs indicated as "Hypotension-related event" or "Combination of the above two events ("Hypotension-related event" and "Hyperkalaemia-related event")" in the CRF.

- Other investigation items
 - Renal impairment-related events

Renal impairment-related events are events coded as one of the following preferred terms (PTs):

Acute kidney injury, Chronic kidney disease, Renal failure, or Renal impairment.

- Blood pressure (systolic, diastolic)
- Body weight
- Laboratory tests (serum creatinine, serum potassium, BUN)

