8.2.3. Safety Analysis

8.2.3.1. Adverse Reactions

• All Adverse Reactions

Adverse reactions will be summarized by system organ class (SOC) and preferred term (PT) in terms of number and proportion of patients.

• Serious Adverse Reactions

Serious adverse reactions will be summarized by SOC and PT in terms of number and proportion of patients.

• Details of Adverse Reactions

Adverse reactions will be summarized by each of the categorizations below for each PT in terms of number and proportion of patients:

- Seriousness [serious, non-serious]
- Known/unknown [known, unknown]
- Action taken [permanent discontinuation, temporary discontinuation or dose reduction, others (none, dose increase)]
- Outcome [not recovered, recovered with sequelae, improved, resolved/recovered, unknown, death]

If the same patient experienced the same adverse reaction (of the same PT) more than once, the patient will be counted as follows:

- Seriousness: If the events include both serious and non-serious ones, the patient is counted as a
 patient experiencing a serious reaction.
- Known/unknown: If the events include both known and unknown ones, the patient is counted as
 a patient experiencing an unknown reaction.
- Time to onset (days): The first onset will be counted.
- Action taken: If multiple actions were taken, a single action will be chosen according to the
 order of priority of (1) permanent discontinuation, (2) temporary
 discontinuation/dose reduction, and (3) others (none, dose increase).
- Outcome: The outcome of the last event will be used.

• Major Investigation Items

The major investigation items listed below will be summarized in terms of number and proportion of patients:

- Hyperkalaemia
- Hypotension-related events

In addition, each major investigation item will be summarized by action taken and by outcome for each PT in terms of number and proportion of patients.

• Other Investigation Items

Renal impairment-related events will be summarized in terms of number and proportion of patients. In addition, the events will be summarized by action taken and by outcome for each PT in terms of number and proportion of patients.

• Onset Time of Adverse Reaction

All adverse reactions, hyperkalaemia, hypotension-related events, and renal impairment-related events will be summarized by time of first onset [Appendix A1.1] for each SOC and PT in terms of number of patients.

Relationship Between Concomitant Drugs and Adverse Reactions

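### Non-serious adverse events are compared by renal function only if the physician judged them drug-related; an all-AE comparison by eCLCr should stand beside the adverse-reaction one

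*SAP*

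**What the plan says.** The primary objective is safety in CHF patients with moderate renal impairment (Protocol 6.2, SAP 2.2). Protocol 7.7 calls for a comparison of safety in these patients with other patients, and SAP 5.4 lists eCLCr among the safety subgroups.

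- **Subgroup endpoints (SAP 8.2.3.4).** In each subgroup "the number and proportion of patients experiencing at least one adverse reaction will be presented", with a breakdown by SOC and PT. Risk ratios are planned "for the incidence of adverse reactions (the proportion of patients experiencing adverse reactions) for each of the binary categorizations". The section then says: "Similar subgroup analyses will be performed also for serious adverse reactions and SAEs".
- **What a reaction is (SAP 6.1).** "An adverse reaction is an AE related to study drug as judged by the physician".
- **All AEs (SAP 8.2.3.2).** "AEs will be summarized by SOC and PT in terms of number and proportion of patients". SAEs and non-serious AEs are treated the same way. No split by subgroup is given.
- **Items of interest.** SAP 6.1 defines hyperkalaemia and hypotension-related events on all AEs so flagged in the CRF, and renal impairment-related events by four preferred terms, in each case whatever the attribution. SAP 8.2.3.1 gives overall counts and adds that "each major investigation item will be summarized by action taken and by outcome for each PT", with the same for renal events. It also covers onset time and concomitant drugs, but not renal function.
- **Laboratory data.** Serum potassium and creatinine are safety endpoints in SAP 6.1, but the only variable summarised in SAP 8.2.3.3 is "Blood pressure (systolic, diastolic"). Laboratory values appear as a listing in SAP 9.

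**The concern.** Non-serious hyperkalaemia reaches a table by renal function only after it has passed a causality judgement. The physician who makes that judgement has entered the baseline serum creatinine and graded any renal impairment (Protocol 7.3.1), so knows which group the patient is in.

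The documents make it plausible that the judgement could depend on renal function. Table 4 of the protocol uses serum potassium itself as a criterion for the severity of renal impairment, and Protocol 7.3.10.1 collects factors other than the drug for each hyperkalaemia event. If physicians attribute events at different rates in the two groups, the ratio of reaction rates moves away from the ratio of event rates. For non-serious events no planned summary would let the reader see by how much. The subgroup affected is the one the study was set up to examine.

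**Working it through.** **1. Which endpoints reach a table by eCLCr**

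| Endpoint | Depends on attribution? | Table by eCLCr? |
|---|---|---|
| Adverse reactions | yes | yes (8.2.3.4) |
| Serious adverse reactions | yes | yes (8.2.3.4) |
| SAEs | no | yes (8.2.3.4) |
| All AEs, non-serious AEs | no | no (8.2.3.2, overall only) |
| Hyperkalaemia, hypotension-related and renal items, all-cause | no | no (8.2.3.1, overall only; listings in 9) |
| Serum potassium, creatinine | no | no (listing in 9) |

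The missing cell is the non-serious AE judged unrelated. For serious events, the SAE and serious-reaction tables together give the share judged related in each subgroup.

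**2. The plan's own figures reproduce.** Inputs are from Protocol 7.5.2, for events whose causality could not be ruled out.

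- Hyperkalaemia: 22/261 = 8.4% in moderate renal impairment and 59/1471 = 4.0% in all CHF patients.
- Expected cases: 300 × 0.084 = 25.2 and 350 × 0.084 = 29.4, as stated.
- Range at n = 300: 0.084 ± 1.96 × √(0.084 × 0.916/300) = 5.3% to 11.5%, as stated.

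No stated figure is wrong. The point concerns scope only.

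**3. Illustration of sensitivity to attribution**

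Patients without moderate impairment, by subtraction: 59 − 22 = 37 of 1471 − 261 = 1210, or 3.06%. Risk ratio = (22/261)/(37/1210) = 2.76 (95% CI 1.65 to 4.59).

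Assumptions, none from the documents: these rates (already reaction rates) stand in for all-cause AE rates; the groups are 300 and 700 patients; a share a₁ of events is judged related in moderate impairment and a₀ in the others. Then

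reaction RR = 2.76 × a₁/a₀,

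with SE of log RR = √(1/x₁ − 1/300 + 1/x₀ − 1/700), where x₁ and x₀ are the expected numbers of reactions.

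| a₁ | a₀ | Reaction RR (95% CI) |
|---|---|---|
| 100% | 100% | 2.76 (1.58 to 4.82) |
| 90% | 100% | 2.48 (1.40 to 4.41) |
| 70% | 100% | 1.93 (1.04 to 3.57) |
| 50% | 100% | 1.38 (0.70 to 2.73) |
| 80% | 80% | 2.76 (1.47 to 5.17) |
| 100% | 80% | 3.45 (1.89 to 6.27) |

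Equal shares leave the ratio unchanged; unequal shares move it either way. An all-AE ratio does not depend on a₁ or a₀.

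**The case against.** The case for leaving the plan alone has four parts, and much of it stands.

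1. **Adverse reactions are the protocol's own endpoint.** Protocol 7.7 starts the safety analysis from events whose causal link cannot be ruled out, and the whole sample-size rationale uses such events. A reader might infer that SAP 8.2.3.4 breaks a protocol commitment. It does not: Protocol 7.7 promises a comparison of safety without naming all AEs.
2. **Attribution is not wholly hidden.** A reader might infer that no planned output could show a difference in attribution. The SAE and serious-reaction tables do so for serious events, and SAP 9 pairs a listing of all events with a listing of reactions for the major items and for renal impairment. The non-serious comparison is untabulated, but the data are there.
3. **The threshold for a reaction is low.** Protocol 9.3 asks for a reasonable possibility that the drug caused or contributed to the event, so another possible cause does not by itself make an event unrelated. Hyperkalaemia is moreover expected from the drug's mechanism (Protocol 7.3.10.1). Shares as low as 50% are therefore a stress test, with no support in the documents.
4. **An all-cause ratio is not the truth either.** A reader might infer that any gap between the reaction ratio and the all-AE ratio is bias in the former. With no control arm, a limitation stated in Protocol 7.9, the all-AE ratio includes the background risk of renal disease. Lower attribution in impaired patients could be correct filtering.

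What remains is the empty cell: non-serious AEs judged unrelated are never tabulated by renal function. SAP 5.4, which speaks of safety by subgroup, does not fill it, because 8.2.3.4 is the operative text and names its endpoints.

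**Conclusion.** The gap is real and limited in scope. Non-serious events enter the renal-function comparison only through physician attribution, and the all-cause hyperkalaemia, hypotension-related and renal items have no summary by eCLCr.

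The documents do not establish that attribution differs by renal function, or in which direction. Nor do they say what fraction of hyperkalaemia is non-serious. The illustrated ratios, from 1.38 to 3.45 around 2.76, rest entirely on assumed shares and on reaction rates standing in for all-cause rates. They show sensitivity and do not estimate bias. All tests in the study are exploratory (SAP 4.1), and because risk ratios are tied to binary categorizations while eCLCr has three levels plus unknown, even the adverse-reaction ratio for moderate impairment is not clearly specified.

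This is a worthwhile, cheap improvement on the study's main question. It is not an error in the planned analysis.

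**What to change.** In the SAP 8.2.3.4 sentence that extends the subgroup analyses, add all AEs to the list, alongside serious adverse reactions and SAEs.

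For hyperkalaemia, hypotension-related and renal impairment-related events, add one table by eCLCr category giving:

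- patients with the AE, count and percentage;
- patients with the adverse reaction, count and percentage;
- the percent judged related.

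Present these beside the adverse-reaction comparison, not in place of it. Add a note that, without a control arm, the all-cause comparison includes background risk from renal disease.

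**Cost.** One phrase in the SAP, a few extra tables, and all-cause rates that mix drug and background effects and so need that note. No new data are required: Protocol 7.3.8 already collects AEs regardless of causality, and the subgroup layout exists. SAP versions 6.0 and 7.0 added subgroup analyses with observation already completed, so a late addition is practicable; it should be recorded in the revision history as such.
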